**Table 7-1: Clinical Laboratory Panels**

Hematology	Serum Chemistry	Urinalysis

 
white blood cell count with differential (including at minimum: neutrophils, basophils, eosinophils, lymphocytes, monocytes)
 
red blood cell count
 
hemoglobin
 
hematocrit
 
platelet count
 
MCV
 
	
 
albumin
 
alkaline phosphatase
 
ALT
 
AST
 
BUN
 
calcium
 
carbon dioxide
 
chloride
 
cholesterol
 
creatinine
 
CPK
 
direct bilirubin
 
GGT
 
globulin
 
glucose
 
lactate dehydrogenase
 
magnesium
 
phosphorus
 
potassium
 
sodium
 
total bilirubin
 
total protein
 
uric acid
 
	
 
appearance
 
color
 
pH
 
specific gravity
 
ketones
 
protein
 
glucose
 
bilirubin
 
nitrite
 
urobilinogen
 
occult blood (microscopic examination of sediment will be performed only if the results of the urinalysis dipstick evaluation are positive)
 

Coagulation	Thyroid	

 
INR
 
PT
 
PTT
 
	
 
TSH
 
	
Lipid Panel	Biomarkers	

 
Total cholesterol
 
Triglycerides
 
HDL cholesterol
 
LDL cholesterol
 
	
 
IL-17
 
	

ALT = alanine aminotransferase; AST = aspartate aminotransferase; BUN = blood urea nitrogen; CPK = creatine phosphokinase; GGT = gamma glutamyl transpeptidase; HDL= high density lipoprotein; INR = international normalized ratio; LDL = low density lipoprotein; MCV = mean corpuscular volume; PT = prothrombin time; PTT = partial thromboplastin time; TSH = thyroid-stimulating hormone

Abnormalities in clinical laboratory tests that lead to a change in subject management (e.g., dose delay, discontinuation, requirement for additional medication or monitoring) are considered clinically significant for the purposes of this study, and will be recorded on the AE eCRF page. With the exception of LFTs, laboratory results will be classified using the Toxicity Grading Scale for Healthy Adult and Adolescent Volunteers Enrolled in Preventive Vaccine Clinical Studies (see Appendix A). Laboratory results for ALT, AST, alkaline phosphatase, GGT, and

bilirubin will be classified according to Table 9-2 in Section 9.4. If laboratory values constitute part of an event that meets criteria defining it as serious, the event (and associated laboratory values) must be reported as an SAE (see Section 11.3.1).

#### **7.2.5 12-Lead Electrocardiogram**

Supine 12-lead ECGs will be obtained prior to blood sample collection (tolerance window: -240 minutes to 0 hour).

Digital 12-lead ECG measurements are to be taken with the subject in a supine position and having rested in this position for at least 5 minutes before each reading. The ECG is to be repeated 3 times consecutively within 30 minutes (with a required interval of at least 1 to 2 minutes between ECGs). At each visit, and when possible, the ECG is to be performed immediately prior to any blood sample collection.

The following ECG parameters will be collected: PR interval, RR interval, QRS interval, QT interval, and QTc interval (QTc[F]; Fridericia's correction, see Appendix B for formula). The ECG findings will be evaluated by a qualified physician for the presence of abnormalities (qualitative assessment). The physician will assess each ECG as normal, abnormal/not clinically significant, or abnormal/clinically significant.

Abnormalities in the ECG that lead to a change in subject management (e.g., dose interruption or delay, requirement for additional medication or monitoring) or result in clinical signs and symptoms are considered clinically significant for the purposes of this study and will be recorded on the AE eCRF. If ECG abnormalities meet criteria defining them as serious, they must be reported as an SAE (see Section 11.3.1).

#### **7.2.6 Pregnancy Testing**

Urine pregnancy tests will be collected for women of childbearing potential. Positive results will be confirmed with serum testing.

#### **7.2.7 Randomization**

Following the completion of screening assessments, eligible, consenting subjects will be randomized to 1 of 5 dose cohorts. See Section 5.7 for further details.

### **7.2.8 Punch Biopsy (Optional)**

Punch biopsies will be obtained from at least 75% of the subjects. Subjects have the option to decline the punch biopsy. Punch biopsies will be taken from clear unaffected skin and a selected lesion will be collected predose on Day 1 (Week 1) and from the selected lesion on Day 112 (Week 16). Biopsies will be obtained through a standard punch biopsy procedure. These biopsies will be analyzed for PD markers associated with psoriasis and with Rho Kinase inhibition.

### **7.2.9 Blood Sampling for Pharmacodynamics**

Blood sample collection for PD will be performed at all sites (refer to Table 1-1 for time points). All subjects will have PD blood samples collected over the course of the study. Subjects who elect to continue therapy will also have PD blood samples collected.

For any subject who discontinues prematurely, blood for PD evaluation will be collected at the Early Termination visit.

Samples will be evaluated for the expression of the psoriasis-associated cytokine, IL-17, in plasma. Detailed instructions for sample collection and preparation will be provided in a separate manual.

### **7.2.10 Psoriasis Area and Severity Index Scoring**

The PASI is a measure of the psoriasis disease severity using the average redness, thickness, and scaliness of the lesions (each graded on a 0–4 scale), weighted by the area of involvement

(Wozel et al, 2005). PASI combines the assessment of the severity of lesions and the area affected into a single score in the range 0 (no disease) to 72 (maximal disease).

To score the PASI, the body is divided into 4 sections

- head (H): 10% of a person's skin
- arms (A): 20% of a person's skin
- trunk (T): 30% of a person's skin
- legs (L): 40% of a person's skin

Each of these areas is scored by itself, and then the 4 scores are combined into the final PASI. For each section, the percent of area of skin involved, is estimated and then transformed into a grade from 0 to 6:

- Grade 0: 0% of involved area
- Grade 1: < 10% of involved area
- Grade 2: 10%–29% of involved area
- Grade 3: 30%–49% of involved area
- Grade 4: 50%–69% of involved area
- Grade 5: 70%–89% of involved area
- Grade 6: 90%–100% of involved area

Within each area, the severity is estimated by 3 clinical signs: erythema (redness), induration (thickness), and desquamation (scaling). Severity parameters are measured on a scale of 0 to 4, from none to maximum.

The sum of all 3 severity parameters is then calculated for each section of skin, multiplied by the area score for that area and multiplied by weight of respective section (0.1 for head, 0.2 for arms, 0.3 for body, and 0.4 for legs).

#### **7.2.11 Relative Physician's Global Assessment**

The relative PGA documents the physician's assessment of the subject's psoriasis status (Robinson 2012). Consideration should be given to the percent of body involvement as well as overall induration, scaling, and erythema (refer to Appendix C).

The DLQI is a skin disease-specific instrument designed to assess the impact of the disease on a subject's quality of life (Finlay et al, 1994). Refer to Appendix D for the complete questionnaire.

#### **7.2.12 Photography (Optional)**

Subjects have the option to participate in the photography of selected lesions. The same lesions should be photographed throughout the study. Further information can be found in the Kadmon photography manual.

#### **7.2.13 Study Drug Administration**

Subjects will receive an adequate supply of study drug for the intervals between the visits scheduled for study drug administration. During the double-blind treatment period, study drug will be dispensed in a blinded fashion and each subject will receive 2 tablets to take each morning and 1 tablet to take each evening. During the 32-week continuation period, all subjects will receive open-label 400 mg KD025 QD, as two 200 mg tablets to be taken in the morning.

At each designated visit, subjects will receive the morning dose (2 tablets) of study drug in the clinic. Subjects will self-administer the balance of daily doses of study drug at home.

Each dose of study drug should be taken together with a meal or within 5 minutes of finishing a meal. See Section 9.1 for further information regarding the dosing schedule and Section 9.3 for guidance regarding missed doses.

#### **7.2.14 Subject Drug Diaries**

Subjects will be required to keep study drug diaries in which they will record the date of study drug administrations. These diaries will be dispensed at the Day 1 (Week 1) visit. Final collection will be at Week 16 for those who do not wish to continue into the open-label period. For subjects that complete the open-label treatment period the diary will be collected at the Week 48 visit. For subjects who discontinue the study prematurely, the diary will be collected at the Early-Termination visit. Prior and Concomitant Medications

All concomitant medications, including corticosteroids and changes in corticosteroid usage during the study, will be collected from the time the subject signs the ICF throughout the subject's participation in the study.

### 7.2.15 Adverse Event Assessments

Information regarding the occurrence of AEs will be collected from the time subjects sign the ICF throughout their participation in the study, including a period of 30 days after last dose of study drug.

**Note:** AEs resulting in a subject's permanent discontinuation from the study, regardless of seriousness or relationship to study drug, **MUST** be promptly reported to the sponsor.

See Section 8.2 for stopping rules for this study. Also, if significant increases ( $> 2 \times$  ULN of ALT or AST) in liver enzymes are observed at any time, refer to Section 9.4 for additional information and recommended procedures.

## **8 REMOVING SUBJECTS FROM STUDY**

Every reasonable effort will be made to keep the subject in the study; however, in the event that a subject is withdrawn from the study, every effort will be made by the investigator to complete and report the reasons for withdrawal as thoroughly as possible. This evaluation should include final observations, as required by the protocol at the time of the subject's withdrawal. The reason(s) for termination must be clearly documented on the appropriate page of the eCRF. A termination eCRF must be completed for any subject who is enrolled in the study.

### **8.1 Subject Withdrawal**

A subject's participation in the study may be discontinued for any of the following reasons:

#### **8.1.1 Treatment Discontinuation**

- An AE requires permanent discontinuation of study drug
- Voluntary withdrawal by subject
- Noncompliance to protocol

#### **8.1.2 Study Discontinuation**

In the event of premature discontinuation, every effort should be made to have the subject come to the clinic for an Early-Termination and 30-day Follow-Up visit in order for the investigator to collect all clinical and laboratory data as scheduled. (Refer to Table 1-1, Schedule of Assessments for a complete list of procedures to be performed.) If a subject dies, Kadmon will actively seek to know the date of death.

Subjects who are withdrawn from this study due to toxicity are to be followed until:

- Resolution or stabilization of toxicity
- The subject is lost to follow-up
- The event is otherwise explained

If there is an ongoing toxicity due to KD025, subjects must be followed with appropriate medical management until resolution or stabilization.

A reasonable effort should be made to contact any subject lost to follow-up during the course of the study in order to complete assessments and retrieve any outstanding data. If the subjects are

unreachable by telephone after 3 attempts, a certified registered return receipt letter should be sent requesting that contact be made with the investigator to report updated information.

## **8.2 Stopping Rules**

Stopping criteria will be assessed using the Clinical Symptom Adverse Event Grading scale (Appendix E) and will include clinically significant changes with respect to BP, dyspepsia, nausea or vomiting, or other treatment-emergent AEs that are Grade 2 (moderate) or higher.

### **8.2.1 Adverse Events Stopping Criteria**

- AEs of clinical concern
- Grade 2 (moderate) or higher TEAEs that are determined by the investigator to be possibly, probably, or definitely related to study drug (with the exception of liver-related adverse events, see Section 9.4);
- Clinically significant elevation of ALT or AST. See Section 9.4 for risk management of LFTs changes observed during the study.

### **8.2.2 Blood Pressure Stopping Criteria**

BP is to be measured with the subject in a sitting position according to the guidelines in Section 7.2.4. BP measurements meeting stopping criteria should be repeated once, to confirm the measurement. The repeat measurement will be used to determine whether the subject meets the stopping criteria.

Clinically significant BP decreases will be defined as follows:

- An absolute systolic BP (SBP) < 85 mmHg at any time point, or a decrease > 30 mmHg in SBP from baseline with accompanying symptoms of hypotension at any time point, or an asymptomatic decrease > 30 mmHg from baseline on any 2 consecutive time points

OR

- An absolute diastolic BP (DBP) < 45 mmHg at any time point, or a decrease > 20 mmHg in DBP from baseline with accompanying symptoms of hypotension at any time point, or an asymptomatic decrease > 20 mmHg in DBP from baseline on 2 consecutive time points.

Clinically significant BP increases are defined as:

- An absolute SBP > 180 mmHg at any time point, or an increase > 30 mmHg in SBP from baseline with accompanying symptoms of hypertension at any time point, or an asymptomatic increase > 30 mmHg from baseline on any 2 consecutive time points

OR

- An absolute DBP > 110 mmHg at any time point, or an increase > 20 mmHg in DBP from baseline with accompanying symptoms of hypertension at any time point, or an asymptomatic increase > 20 mmHg in DBP from baseline on 2 consecutive time points.

### 8.3 Study Termination

Kadmon Corporation has the right to terminate or to stop the study at any time. Reasons for study discontinuation may include, but are not limited to the following:

- The incidence or severity of AEs in this or other related studies indicates a potential health hazard to subjects
- Subject enrollment is unsatisfactory
- Drug supply issues
- Data recording is inaccurate or incomplete
- Excessive subject self-withdrawal
- Significant protocol violations (e.g., violation of eligibility criteria, dosing errors, missing data for study endpoint analysis)

### 8.4 Replacements

Subjects withdrawn from the study prior to receiving any study drug will be replaced by enrolling additional subjects into the study.

## 9 STUDY DRUG

### 9.1 Dose and Schedule of Study Drug and Reference Therapy

After the completion and review of all screening and baseline procedures, eligible, consenting subjects will be randomly assigned to 1 of 5 dose cohorts in a 1:1:1:1:1 manner (see Table 9-1). Study drug will be orally administered in a double-blind fashion for 16 weeks.

Study drug will be dispensed by the site pharmacist, or designee. KD025 will be supplied as 200-mg tablets. Doses to be studied are 200 mg KD025 QD, 200 mg KD025 BID, 400 mg KD025 QD, and KD025 600 mg/day (administered as 400 mg in the morning and 200 mg in the evening). Placebo will be supplied as matching tablets.

**Table 9-1 Dosing Cohorts**

Cohort	No. of Subjects	Dose Regimen
Cohort 1	22 subjects	200 mg KD025 QD (subjects will receive 1 KD025 200 mg and 1 matching placebo tablet in the morning and a matching placebo in the evening)
Cohort 2	22 subjects	200 mg KD025 BID (subjects will receive 1 KD025 200 mg and 1 matching placebo tablet in the morning and KD025 200 mg in the evening)
Cohort 3	22 subjects	400 mg KD025 QD (subjects will receive 2 KD025 200 mg tablets in the morning and a matching placebo in the evening)
Cohort 4	22 subjects	600 mg/day KD025 (subjects will receive 2 KD025 200 mg tablets in the morning and 1 KD025 200 mg in the evening)
Cohort 5	22 subjects	Control (subjects will receive 2 matching placebo tablets in the morning and 1 matching placebo tablet in the evening)

Each dose of study drug should be taken together with a meal or within 5 minutes of finishing a meal.

Subjects will return to the clinic as outlined in the Schedule of Assessments (Table 1-1), and will receive the morning dose of study drug (2 tablets) during visits when PD samples are to be drawn. Subjects will self-administer the balance of daily doses of study drug at home.

## 9.2 32-Week Open-Label KD025 Therapy (Week 16 through Week 48)

Subjects randomized to KD025 or placebo will have the option to continue 400 mg of KD025 QD treatment for an additional 32 weeks in the open-label treatment period.

## 9.3 Missed Doses

- Subjects should make every effort to take the study drug at the same scheduled times daily, morning and evening. In the event that the subject misses the planned dose of study drug, the following protocol should be followed: If less than 6 hours of time have elapsed after the scheduled dose, the drug should be taken and the subject should resume their dosing schedule with the next dose.
- If more than 6 hours of time have elapsed after the scheduled dose, the dose should be skipped. The subject should resume the regular planned dosing schedule.

If the subject skips more than 7 consecutive days of drug, the subject should be discontinued from the study. If the subject cannot take KD025 for more than 7 consecutive days due to a toxicity, the subject is allowed to re-start study drug.

## 9.4 Evaluation of Liver-Related Blood Tests

Clinically significant elevations of liver-related blood tests as defined below require immediate drug termination.

1. ALT or AST  $> 5 \times$ ULN
2. ALT or AST  $> 3 \times$ ULN and (total bilirubin  $> 2 \times$ ULN or INR  $> 1.5$ )
3. ALT or AST  $> 3 \times$ ULN with the appearance of fatigue, nausea, vomiting, right upper quadrant pain or tenderness, fever, rash, and/or eosinophilia ( $> 5\%$ )
4. If the total bilirubin is  $> 2 \times$ ULN then obtain direct bilirubin

If ALT or AST  $> 2.0 \times$ ULN, the subject should remain on study drug with **close observation** which includes:

1. Repeating liver enzyme, every 48 to 72 hours  
(Frequency of retesting can decrease to once a week or less if abnormalities stabilize or the study drug has been discontinued and the subject is asymptomatic.)
2. Obtaining a more detailed history of symptoms and prior or concurrent diseases

3. Obtaining a history of concomitant drug use (including nonprescription medications and herbal and dietary supplement preparations), alcohol use, recreational drug use, and special diets
4. Ruling out acute viral hepatitis types A, B, and C
5. Obtaining a history of exposure to environmental chemical agents

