**Table 1-1 Schedule of Assessments**

Assessments	Screening	Double-Blind Treatment Period					32-Week Open-Label Continuation Period						Unscheduled or Early Termination b Visit (±3 days)	30-Day Follow-Up c (±3 days)
		Week 1	Week 4	Week 8	Week 12	Week 16 a	Week 20	Week 24	Week 30	Week 36	Week 42	Week 48		
Visit	1	2	3	4	5	6	7	8	9	10	11	12		
Day	-28 to -1	1 (Baseline)	28 (±3 days)	56 (±3 days)	84 (±3 days)	112 (±3 days)	140 (±3 days)	168 (±3 days)	210 (±3 days)	252 (±3 days)	294 (±3 days)	336 (±3 days)		
Informed consent	X													
Demographics and Medical history	X													
Physical examination d	X	X				X		X		X		X	X	X
Vital signs e	X	X	X	X	X	X	X	X	X	X	X	X	X	X
Hematology and serum chemistry f	X g	X	X	X	X	X	X	X	X	X	X	X	X	X
Lipid panel h	X g	X				X	X	X		X		X	X	X
PT, PTT, INR	X g	X				X	X	X		X		X	X	X
TSH	X g	X				X	X	X		X		X	X	X
Urinalysis	X g	X	X	X	X	X	X	X	X	X	X	X	X	X
Supine 12-Lead ECG i	X	X				X						X	X	
Pregnancy test j	X	X	X	X	X	X	X	X	X	X	X	X	X	X
Randomization k		X												
Photographs (optional) l		X				X						X	X	X
Punch Biopsy (optional) m		X				X								
PD whole blood sample n		X		X		X						X	X	X

Assessments	Screening	Double-Blind Treatment Period					32-Week Open-Label Continuation Period						Unscheduled or Early Termination b Visit (±3 days)	30-Day Follow-Up c (±3 days)
		Week 1	Week 4	Week 8	Week 12	Week 16 a	Week 20	Week 24	Week 30	Week 36	Week 42	Week 48		
Visit	1	2	3	4	5	6	7	8	9	10	11	12		
Day	-28 to -1	1 (Baseline)	28 (±3 days)	56 (±3 days)	84 (±3 days)	112 (±3 days)	140 (±3 days)	168 (±3 days)	210 (±3 days)	252 (±3 days)	294 (±3 days)	336 (±3 days)		
PASI Scoring	X e	X	X	X	X	X		X		X		X	X	
PGA Scoring		X	X	X	X	X		X		X		X	X	
DLQI	X	X	X	X	X	X		X		X		X	X	
Study drug administration p		X		X		X						X		
Dispense/Collect study drug Diary q		X				X						X	X	
Concomitant medications		To be collected from the date that the informed consent form is signed until 30 days after last dose of study drug.												
Adverse events														

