DLQI = Dermatology Life Quality Index; ECG = electrocardiogram; INR = international normalized ratio; PASI = Psoriasis Area and Severity Index; PD = pharmacodynamics; PGA = Physicians Global Assessment; PT = prothrombin time; PTT = partial thromboplastin time; TSH = thyroid-stimulating hormone.

- a. After Week 16 assessments in the double-blind treatment period, subjects will be given the option to receive KD025 400 mg QD for an additional 32-weeks in an open-label treatment period (end of week 16 assessments through week 48).
- b. Unscheduled visits and the assessments performed are at the investigator's discretion, but may include any or all of those listed. An Early-Termination visit will be scheduled for all subjects who discontinue prematurely from study drug during the double-blind or open-label treatment periods and procedures are to be conducted immediately upon discontinuation.
- c. For all subjects, including those who discontinue from the study prematurely, a Follow-Up visit should occur 30 days (± 3 days) after their last dose of study drug.
- d. Physical examinations will include weight. Height is to be collected only at the Screening visit.
- e. Vital sign measurements will include sitting blood pressure (BP), heart rate, respiratory rate, and temperature after 5 minutes of rest. Refer to Section 7.2.4 for appropriate BP measuring technique.
- f. Refer to Section 7.2.5 for a complete list of required hematology and serum chemistry assessments. If increases in liver enzymes are observed at any time in a subject, refer to Section 9.4.
- g. If laboratory assessments are done within 14 days of Day 1, they do not need to be repeated on Day 1.

- 
- h. Lipid panel to include total cholesterol, triglycerides, high density lipoprotein (HDL) cholesterol, and low density lipoprotein (LDL) cholesterol.
  - i. ECGs are to be performed immediately prior to blood sample collection (tolerance window: -240 minutes to 0 hour) and to be obtained in triplicate after 5 minutes of resting in the supine position (see Section 7.2.5 for additional information).
  - j. Pregnancy tests will be done using urine samples in women of childbearing potential. Subject must have a negative urine pregnancy test documented within the 24-hour period prior to the first dose of study drug. Confirm with serum testing if urine sample is positive.

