#### **4.3 Previous Clinical Experience with KD025**

A Phase 1 fed or fasted study (KD025-105) was conducted to evaluate the food effect as well as to further evaluate the safety and PK of a single 500-mg dose of KD025 administered orally to fed and fasted healthy males.

Study results showed approximately a 3-fold higher exposure (maximum serum concentration [ $C_{max}$ ] and area under the curve [AUC]) in the fed state compared with the fasted state. There were no treatment emergent adverse events (TEAEs) and no treatment-related AEs were reported in any subject after receiving KD025 in either the fed or fasted state. There were no clinically relevant changes in vital signs, physical examination (PE) findings, or electrocardiogram (ECG) parameters. There were no clinically relevant changes and no clinically meaningful trends in hematology, chemistry, and urinalysis laboratory results attributable to study drug during this study. Plasma concentrations achieved in this study were comparable to plasma levels achieved in previous studies at similar dose levels, where breakfast was provided immediately after dose administration. These studies support dosing KD025 with food.

KD025-205 was a Phase 2a, open-label study in 8 adult subjects with moderately severe psoriasis vulgaris who have failed first-line therapy. As with the other studies, 200 mg QD KD025 administered daily for 28 days was generally safe and well tolerated.

KD025-206 was a Phase 2a, open-label, dose-finding study in 36 adult subjects with moderately severe psoriasis vulgaris who have failed first-line therapy. The study was a 3-month, open-label study with 3 cohorts (200 mg BID, 400 mg QD, and 400 mg BID). KD025 was well tolerated in all subjects and demonstrated activity as measured by PASI. The only adverse experience was related to elevated alanine aminotransferase (ALT)/ aspartate aminotransferase (AST) levels in approximately 20% of the subjects. The KD025 400-mg BID group showed the highest (Grade 3) elevations. The 400-mg BID dose will not be pursued in future studies.

The Investigator's Brochure (IB) 2015 includes additional nonclinical and clinical information about this agent.

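### The liver termination rule in Section 9.4 uses INR, but INR is not required at 5 of 10 post-baseline treatment visits or in the repeat testing, and item 4 of the same list does not match its heading

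*Protocol*

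**What the plan says.** Protocol Section 9.4 introduces four numbered items with "Clinically significant elevations of liver-related blood tests as defined below require immediate drug termination". In substance they are:

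1. ALT or AST above 5 × ULN.
2. ALT or AST above 3 × ULN with either total bilirubin above 2 × ULN or INR above 1.5.
3. ALT or AST above 3 × ULN with any of a list of symptoms and signs, including eosinophilia above 5%.
4. Total bilirubin above 2 × ULN, for which the stated action is to obtain a direct bilirubin.

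A second list in 9.4 covers ALT or AST above 2 × ULN. It keeps the subject on study drug under close observation. Its only laboratory monitoring step is "Repeating liver enzyme, every 48 to 72 hours"; the rest is history-taking and excluding viral hepatitis.

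Two other places send the site to 9.4. Footnote f of Table 1-1 says "If increases in liver enzymes are observed at any time in a subject, refer to Section 9.4". Section 8.2.1 exempts liver-related events from its Grade 2 criterion and adds, for ALT or AST elevations, "See Section 9.4 for risk management of LFTs changes observed during the study".

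In Table 1-1 the row "Hematology and serum chemistry" is marked at every visit. The coagulation row, which contains INR, is not. For unscheduled visits, footnote b leaves the choice of tests to the investigator, "but may include any or all of those listed".

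**The concern.** A mandatory termination rule should have its inputs measured whenever it is to be applied. Section 9.4 is meant to operate at any time, yet one of its inputs is not collected at several visits where the enzymes that trigger it are collected.

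The missing value is not neutral. If ALT or AST lies above 3 and up to 5 × ULN and nothing else in the list is met, the text that remains in force is the close-observation paragraph, which continues the drug. A subject whose INR would have met criterion 2 is then handled as if it had not, unless the investigator happened to order the test.

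Item 4 raises a second question of the same kind. A site that reads the heading would stop drug for an isolated bilirubin above 2 × ULN. A site that reads the item would order a test and continue. Both readings are open on the text.

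**Working it through.** No figure in the plan underlies this point, so there is none to reproduce. The check sets Table 1-1 beside Section 9.4.

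**Step 1. Which inputs are scheduled when.** Chemistry (ALT, AST, total and direct bilirubin) and hematology (differential with eosinophils) are as listed in Table 7-1. Visit marks and days are from Table 1-1.

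| Visit | Day | ALT, AST, bilirubin, eosinophils | INR |
|---|---|---|---|
| Week 4 | 28 | yes | no |
| Week 8 | 56 | yes | no |
| Week 12 | 84 | yes | no |
| Week 16 | 112 | yes | yes |
| Week 20 | 140 | yes | yes |
| Week 24 | 168 | yes | yes |
| Week 30 | 210 | yes | no |
| Week 36 | 252 | yes | yes |
| Week 42 | 294 | yes | no |
| Week 48 | 336 | yes | yes |

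Both sets are also marked at screening, Day 1, the Unscheduled or Early Termination column and the 30-day follow-up.

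- Post-baseline treatment visits without INR: 5 of 10.
- Double-blind period: 3 of 4 (Weeks 4, 8, 12).
- Open-label period: 2 of 6 (Weeks 30, 42).

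**Step 2. Length of the gaps between scheduled INR values.**

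- Double-blind: 112 − 1 = 111 days, or 115 − 1 = 114 days with the +3-day window.
- Footnote g allows "If laboratory assessments are done within 14 days of Day 1, they do not need to be repeated on Day 1". With the last INR taken 14 days before Day 1, the gap is 14 + 111 = 125 days.
- Open-label: 252 − 168 = 84 days, then 336 − 252 = 84 days.

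**Step 3. Which parts of 9.4 are affected at a visit without INR.**

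| Part of 9.4 | Inputs | Assessable from scheduled tests and symptoms? |
|---|---|---|
| Criterion 1 | ALT, AST | yes |
| Criterion 2, bilirubin limb | ALT, AST, total bilirubin | yes |
| Criterion 2, INR limb | ALT, AST, INR | no |
| Criterion 3 | ALT, AST, symptoms, eosinophils | yes |

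**Step 4. The path of an affected subject.** Take ALT above 3 and up to 5 × ULN at Week 8, bilirubin at or below 2 × ULN, and no listed symptom or sign. Criterion 1, the bilirubin limb and criterion 3 are not met. The INR limb cannot be judged from anything the schedule requires. The close-observation paragraph applies, because ALT is above 2 × ULN. Its repeat testing names liver enzymes only, so it does not supply the INR. It does not name bilirubin either, so between scheduled visits the bilirubin limb has the same weakness.

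**Step 5. Item 4 against its heading.** The heading makes every listed elevation a reason to terminate. The item names an elevation and orders a test. Table 7-1 already includes direct bilirubin in the chemistry panel drawn at every visit, so as a testing instruction the item adds little at scheduled visits. The list does not say which of the two actions is meant.

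**The case against.** The strongest reply is that the INR is within reach. The coagulation row is marked in the Unscheduled or Early Termination column. Footnote b and Section 7.1.5 allow any listed test at such a visit, and Section 7.1.1 lets the sponsor as well as the investigator call for one. A subject above 2 × ULN is being retested every few days anyway, and the close-observation list is worded as inclusive, not closed. This stands: a reader might infer that the rule cannot operate on INR at these visits, and that is too strong. What remains is that nothing requires the test.

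The reply also bounds the problem correctly. Only one limb of one criterion lacks a scheduled input. In Section 8.2.1 the liver exception attaches to the Grade 2 criterion alone; the separate criterion for adverse events of clinical concern has no such exception, so an investigator has another route to stop drug. Section 9.4 also points to the Investigator's Brochure for further guidance, which is not among these documents.

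Three further inferences are tempting and not supported:

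- **That the gap falls when liver elevations are most expected.** Section 4.3 describes a 3-month psoriasis study with raised ALT or "aspartate aminotransferase (AST) levels in approximately 20% of the subjects". Its length resembles Weeks 1 to 12 here, but no onset times are given, and nothing points to Weeks 30 or 42.
- **That this 20% sizes the problem.** It counts subjects with some elevation, without a threshold of 2 or 3 × ULN. It also includes a 400 mg BID cohort that had the highest elevations and is not studied here.
- **That site differences in ordering INR would shift PASI 75.** SAP Section 3.8.1 does count subjects without a Week 16 assessment as failures, but no figure shows that so narrow a group could move the result.

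On item 4, the reply is that it is simply an instruction under the wrong heading. That may be what was intended, but the text does not settle it.

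**Conclusion.** The mismatch is real and narrow. At 5 of 10 post-baseline treatment visits, including 3 of 4 in the double-blind period, the INR limb of criterion 2 rests on a discretionary test, and the repeat testing does not close the gap. Criteria 1 and 3 and the bilirubin limb remain assessable at every scheduled visit. Item 4 is a separate inconsistency between a heading and its content.

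The number of subjects who would reach the INR limb is not given and cannot be derived from the documents. The conclusion rests on the Table 1-1 marks as reproduced in the protocol and on 9.4 as written. It assumes no overriding instruction in the Investigator's Brochure. It deserves correction because the rule is a mandatory safety rule and the change is cheap, not because a large effect has been shown.

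**What to change.** Reconcile Section 9.4 with Table 1-1 and with its own repeat testing, so that each laboratory value the termination rule uses is available whenever the rule is applied. Reconcile item 4 with its heading so that the list states one action for total bilirubin above 2 × ULN. The sponsor's medical team should decide the clinical content of both changes; this review does not propose a rule.

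The cost is protocol wording and, depending on what the medical team chooses, an added assay at blood draws that already take place. An amendment helps only subjects still on study drug when it takes effect. The documents do not say how many that is.
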